6.2.6.1. Reported Post Study Data

Case Report Forms will be used by the CRO to collect and organize data. All data collected during the investigational study will be compiled by the CRO and securely stored by the Sponsor. Data collected will be captured and archived using a per-protocol approach.

The following table provides a list of the reported primary outcomes, as evidenced by the study. Data subgroup analysis following the completion of the study and performance data analysis reported by:

- Age (22-50 vs. 51+)
- Sex assigned at birth (M/F)
- Band size (micro vs. standard)
- Band detachment events, including duration of detachment
- Body location of band placement
- Mechanism of device used (automatic vs. manual)

Data Collected	Description
Proper band placement	Source: Visit 1, Investigator Records STR study device bands will be placed on up to two (2) skin tag(s) by the Investigator. Source: eDiary Participant will upload a photo(s) of the banded skin tag(s) in the eDiary at the Visit 1 in-clinic visit.

Efficacy of skin tag removal	Source: Days 2-2 O, Case Report Forms and Subject eDiary The total number of skin tags treated and those successfully removed by use of the STR study device will be compiled and reported. In all cases, the removal rate will be categorized by skin tag size (micro or standard) and body location as well as subject demographics
Safety and Potential Health Impacts	Source: Case Report Forms and Subject eDiary There are not any serious adverse effects anticipated with this study potential non-serious side effects during the use of the STR study device are as follows and will be collected: Irritation Tenderness Pigment change Scarring Less common but potential side effects that need to be collected and addressed are: Infection Redness or swelling at the base of tag Bleeding Pain Delayed healing (greater than 14 days after tag falling off/removal) Hypertrophic or Keloid scarring Other (as defined/described in the eDiary manual) General use comments by the subjects, including photos depicting the progression of the skin tag(s) treatment and after the tag has fallen of Only adverse events associated with the device will be recorded and documented as Adverse Device Effects (ADEs).

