6.1. Purpose and Study Arms

This pivotal investigational study is designed to evaluate the safety and efficacy of a skin tag removal (STR) study device. This is a non-significant risk interventional clinical study that will be conducted by a Clinical Research Organization (CRO) with a licensed dermatologist(s) to serve as Principal Investigator. There are two arms of the study that are only differentiated by the type of STR study device used; arm 1 will be conducted using the manual version, and arm 2 will use the automatic version.

After consultation with the FDA, the Sponsor has modified the original protocol to include the following changes:

- Exclusion of all skin tags located around the eye, on the eyelid, or the groin area (6.2.1)
- Clarification of covered medical expenses while enrolled in the study (6.2.4)
- Protocol includes updated exclusion conditions (excluding those with known hypertrophic scarring or keloid scarring)
- Protocol includes the addition of an electronic daily diary for all participants
- A study was conducted to power the investigation for biostatistical relevance properly (please see the report in the Reference section). The conditions for power analysis were:
 - The primary endpoint is the removal of the skin tag (effectiveness)
 - The observed percentage of successful removal is 60%; i.e. 60% of the skin tags treated are expected to be successfully removed with use of the device
 - A 95% Confidence Interval (CI) was used to determine the number of subjects necessary for participation

Determination: if a successful clinical trial is established at 60% of treated skin tags removed, a study powered with 200 treated tags will have a 95% confidence interval of 5.5%

The power analysis determined that the sponsor should enroll enough subjects to treat a total of 200 skin tags. Typically, patients seeking skin tag removal have from 1 to 5 tags that could be treated for removal, however, for this study, only a maximum of 2 tags per person will be treated. Therefore, the number of tags for intention to treat (ITT) in each arm is 100 for a study total of 200 tags. This approach will ensure that the study has been powered to a 95% confidence interval of 5.5%.

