Approximately two thirds of the subjects in each arm are to receive micro bands (2-6 mm skin tags treated), while the other one third is to receive standard size bands (4-6mm size skin tags treated). The PI will manage the number of treated skin tags such that a variety of locations on the body (face, neck, arms, and torso) are represented in the study.

Under Protocol Version 1:

Arms	Assigned Interventions
Arm 1 – Manual Version Goal: successful removal of 60% of the skin tags treated with the STR device. Subjects will have up to two (2) tags treated, therefore, 50–100 subjects are anticipated for this arm. A total of 100 skin tags is the ITT (intention to treat).	Subject treatment data collected on: • Band size; 2-4mm (micro), or 4-6mm (standard) • Subject pool divided ~equally by band size • All skin tags will be banded by a healthcare professional
Arm 2 – Auto Version Goal: successful removal of 60% of the skin tags treated with the STR device. Subjects will have up to two (2) tags treated, therefore, 50-100 subjects are anticipated for this arm. A total of 100 skin tags is the ITT (intention to treat).	Subject treatment data collected on: • Band size; 2-4mm (micro), or 4-6mm (standard) • Subject pool divided ~equally by band size • All skin tags will be banded by a healthcare professional

Under Protocol Version 2:

Arms	Assigned Interventions
Arm 1 – Manual Version Goal: successful removal of 60% of the skin tags treated with the STR device. Subjects will have up to two (2) tags treated, therefore, 50–100 subjects are anticipated for this arm. A total of 100 skin tags is the ITT (intention to treat).	Subject treatment data collected on: Tag size; 4-6 mm (micro band) All skin tags will be banded by a healthcare professional

Arm 2 - Auto Version

Goal: successful removal of 60% of the skin tags treated with the STR device. Subjects will have up to two (2) tags treated, therefore, 50-100 subjects are anticipated for this arm. A total of 100 skin tags is the ITT (intention to treat).

Subject treatment data collected on:

- Tag size; 4-6 mm (micro band)
- All skin tags will be banded by a healthcare professional licensed dermatologist

For subjects meeting the inclusion/exclusion criteria and entering the study and having two skin tags being treated as a part of this study, please see the study design details on how both skin tags are to be treated in Section 6.2 below.

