Therefore, the total intention to treat (ITT) is 200 skin tags for arms 1 and 2 combined. If the study is completed with subjects only having one skin tag treated, then the study would need to recruit 200 subjects. If each subject had two skin tags treated, only 100 subjects would need to be recruited. It is anticipated that between 100 and 200 subjects will be required to treat a total of 200 skin tags.

The figures below depict how the total subject pool would be divided into the two arms under both versions of the protocol, where "N" is the number of subjects:

Under Protocol Version 1: Figure 1

[figure not shown]

Figure 1: Breakdown of subjects into each arm and size of band used to be stratified as equally as possible in the targeting of ~200 treated skin tags.

[figure not shown]

Figure 2: Breakdown of subjects into each arm to be stratified as equally as possible in the targeting of ~200 treated skin tags.

Once enrolled in the study, the Investigator will assign an STR version for use (manual/ automatic . Only the micro-sized band will be used in this version of the protocol, and only skin tags measuring 4–6mm at the base will be eligible for treatment. The Investigator will also review the subject's skin tags and agree with the subject on the body location and skin tag(s) that will be treated (see exclusion criteria) . The Investigator will also verify that the skin tag does not present a morphology representing implications of cancerous tissue. After signing informed consent and reviewing device lab,eling as well as determining eligibility , the subject will then have the band(s) placed on the skin tag(s) by the healthcare professional.

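### Does the phrase 'per-protocol approach' in Section 6.2.6.1 commit the removal rate to a per-protocol analysis set?

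*Protocol*

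**What the plan says.** The sentence is in Protocol Section 6.2.6.1 (Reported Post Study Data): "Data collected will be captured and archived using a per-protocol approach". The paragraph opens with "Case Report Forms will be used by the CRO to collect and organize data". Its next sentence says that all data collected in the study are compiled by the CRO and stored by the sponsor. The sentence at issue comes third and closes the paragraph.

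The same section then sets out what is reported. The efficacy row of its table reads: "The total number of skin tags treated and those successfully removed by use of the STR study device will be compiled and reported". The list of subgroup reports includes "Band detachment events, including duration of detachment".

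Section 6.1 gives each arm the same target: "Goal: successful removal of 60% of the skin tags treated with the STR device". It sets the planned size as follows: "the number of tags for intention to treat (ITT) in each arm is 100 for a study total of 200 tags". Section 6.2.1 repeats this: "the total intention to treat (ITT) is 200 skin tags for arms 1 and 2 combined".

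Two places allow withdrawal after band loss. Section 6.2.3 says a participant who cannot arrange rebanding within 3 business days may be withdrawn. Section 11.2 treats failure to arrange rebanding as non-compliance that may end participation, and requires every withdrawal and its reason to be documented.

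**The concern.** Per-protocol is the standard name for an analysis restricted to participants who followed the protocol. Here the term stands directly before the primary outcome reporting, in a protocol that also defines a kind of non-compliance, namely not arranging rebanding after the band comes off. Put together, the two could suggest that tags of participants withdrawn after band loss leave the denominator.

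That would be a serious choice in this design. The primary result is an absolute removal rate set against a 60% goal, with no untreated comparison to absorb a shift. Band loss is a matter of device performance, so tags excluded because of it would probably be mostly unremoved. Leaving them out would raise the reported rate.

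**Working it through.** The question is which denominator the text fixes, so the relevant places are set side by side first. The arithmetic then shows what depends on the answer.

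**1. What the sentence governs.** Its verbs are captured and archived; it says nothing of analysing. The sentence before it says that all collected data are compiled. If per-protocol meant excluding non-compliant participants at capture or archiving, the two sentences would conflict. Read as *in the way this protocol specifies*, they agree.

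**2. Denominators the protocol states.**

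| Place | Quantity | Denominator |
|---|---|---|
| Section 6.1, conditions for the power analysis | expected removal, 60% | tags treated |
| Section 6.1, determination of study success | 60% removed | treated tags |
| Section 6.1, goal of each arm | 60% removed | tags treated |
| Section 6.2.6.1, efficacy row | tags treated and tags removed | tags treated |

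Section 2.2 speaks of the proportion of tags removed within 20 days and names no other denominator.

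**3. Planned total.** Sections 6.1 and 6.2.1 give 100 tags per arm and 200 overall: 100 + 100 = 200, which agrees. The 60% goal is then 0.60 × 200 = 120 tags overall, or 0.60 × 100 = 60 per arm.

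**4. Exclusion rules.** No section defines a per-protocol set. Sections 6.2.3 and 11.2 say when a participant may be withdrawn; neither says that the tag leaves the rate. Performance is also to be reported by band detachment events, which requires tags with band loss to be kept in the data. The rationale column of the version table gives the same purpose for rebanding: to keep participant data when the device fails.

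**5. What the other reading would do.** This is illustration only.

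One tag left out, starting from exactly 60%:

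- one unremoved tag, overall: 120/199 = 60.3% (+0.3 points)
- one unremoved tag, one arm: 60/99 = 60.6% (+0.6 points)
- one removed tag, overall: 119/199 = 59.8% (−0.2 points)
- one removed tag, one arm: 59/99 = 59.6% (−0.4 points)

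For a larger exclusion, let w be the share of tags withdrawn and assume that all of them are unremoved. A reported 60% then needs 0.60 × 200 × (1 − w) removed tags, which as a share of treated tags is 0.60 × (1 − w):

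| Assumed w | Reported as 60% | Share of all treated |
|---|---|---|
| 5% | 114/190 | 114/200 = 57% |
| 10% | 108/180 | 108/200 = 54% |
| 15% | 102/170 | 102/200 = 51% |
| 20% | 96/160 | 96/200 = 48% |
| 25% | 90/150 | 90/200 = 45% |

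The protocol gives no detachment or withdrawal rate, so w is an assumption throughout. Under the denominators in step 2, none of these shifts arises.

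**The case for a change.** The strongest contrary case is that a technical term in a reporting section should be taken in its technical sense. The protocol supplies a group that would fit it: participants non-compliant with rebanding under Section 11.2. The label ITT does not rule this out by itself, because Sections 6.1 and 6.2.1 use it as a planned number of tags and not as a rule for keeping withdrawn participants in the analysis. The protocol also never says outright that a withdrawn tag stays in the denominator. With a single rate held against 60%, one could argue that the denominator should be beyond dispute.

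Part of this stands. The term is an unfortunate one for a sentence about data handling, and ITT is used loosely. The protocol is indeed silent on how tags of withdrawn participants are scored. But that silence concerns analysis sets and the handling of missing outcomes, which a protocol commonly leaves to the SAP, and the SAP is not at hand. It is not a contradiction in the protocol. The technical reading also needs the sentence to do something its verbs do not say, against the sentence before it and against the efficacy row in the same section.

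**Conclusion.** The concern does not hold. The sentence describes how data are recorded and kept, and it sets no analysis population. The removal rate that the protocol describes is removed tags over treated tags, with 60% equal to 120 of 200 overall or 60 of 100 in an arm. The effect of the phrase on any planned figure is zero.

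This rests on two things visible in the text: every denominator stated for removal is treated tags, and no section removes a tag from the rate. It does not assume anything about the SAP. If a SAP defined its primary analysis set by compliance with rebanding, that would be a matter to raise against the SAP. What remains here is an editorial preference about one term.

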Clinical Trial Protocol

Title of study: Skin Tag Removal Device; A Clinical Study to Determine Outcomes of Treating Adults with Acrochordons (Skin Tags)

NCT06463613

Date: 06/05/2025

Clinical Investigation Protocol

Title: Skin Tag Removal Device; A Clinical Study to Determine

Outcomes of Treating Adults with Acrochordons (Skin Tags)

Protocol: UKI-001

Sponsor: UK Innovations GP LTD

Version: 2

Date: TBD

Confidentiality Statement

This document contains confidential information that must not be disclosed to anyone other than the Sponsor, the Investigator Team, HRA, host organization, and members of the Research Ethics Committee and Regulatory Authorities unless authorized to do so.

Trial Title:	Skin Tag Removal Device; A Clinical Study to Determine Outcomes of Treating

Adults with Acrochordons (Skin Tags)

Protocol Number: UKI-001

Protocol Version: 2

Protocol Date: TBD

Protocol signature page

The undersigned has read and understood the trial protocol detailed above and agrees to conduct the trial in compliance with the protocol.

Principal Investigator Name	Principal Investigator Signature	Date	
(Please print)			

Protocol Section	Protocol Version 1	Protocol Version 2	Rationale
Section 3.1-3.2, 4, 6.2.1-6.2.3	Use of micro STR on 2-4 mm skin tags	Use of micro STR on approximately 4-6mm skin tags	The micro STR band has not reached the desired level of efficacy on 2-4mm skin tags per use under protocol version 1. The Sponsor recommends the use of a micro STR band to be placed on larger skin tags, 4-6mm, where they may be more effective at restricting blood flow to the skin tag and removing the tag.
Section 6.2.4, 6.2.6	Daily eDiaries Day 1-10	Daily eDiaries at screening visit, Day 1-20	An eDiary has been added to the screening visit to capture a photo of the skin tag at the time of banding. The number of daily diaries have been extended to 20 days to allow tracking for skin tags which may fall off after day 10.
Section 6.2.4	Virtual Visit 2 window Day 5-8	Virtual Visit 2 window Day 5-9	Visit window was extended to allow for more time to conduct the visit with no impact to patient safety
Section 6.2.4	Virtual Visit 3 window Day 11-14	Virtual Visit 3 window Day 21-24	The visit was moved to one day after the last daily diary completed by participants, which is now day 20 under protocol version 2.

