Section 6.2.1	6.2.1 Stratification schematic to reflect 1:1 ratio of micro:standard STR device type	6.2.1 Stratification schematic to reflect 3:1 ratio of micro:standard STR device type	Due to micro and standard devices not reaching desired level of success in removing skin tags for 2-4 and 4-6 mm, respectively, the new recruitment efforts will focus on large skin tags and use of the micro device only
Section 4	Indications for use statement per device type	General indications for use statement to be determined upon completion of the study	Indications for use have been updated to be determined upon competition of the study
Section 6.2.1	80% compliance for eDiary completion to	participant payment of \$10 per eDiary completed	Participant compensation has been changed from overall compliance calculation to daily diary completion

			Tieaitii
	receive \$100 payment		to increase retention & eDiary completion through Day 20
Sections 6.2.3; 6.2.6	Rebanding not permitted; participants were withdrawn if device detached prematurely.	Participants may receive up to two rebanding visits per skin tag at the site in the event of premature device detachment. Rebanding details (e.g., timing, outcome) will be captured in the eDiary.	To allow controlled reapplication of the device and preserve participant data in cases of device failure, while maintaining consistency in study execution and analysis.
Section 6.2.3	No bandage was used after device placement.	A small adhesive bandage is applied at the screening visit to cover the banded skin tag. Participants receive approximately 20 bandages and instructions for replacement as needed.	To reduce risk of premature band detachment due to friction from clothing and improve retention of the device throughout the study period.
Section 6.2.1	No guidance on re- enrollment of prior participants	Participants previously enrolled may be re- enrolled if a different, previously unbanded skin tag is selected	To allow enrollment of individuals who meet inclusion criteria and had a device failure in a prior protocol version, without compromising data integrity
Sections 6.1, 14	The observed percentage of successful removal is 80%	The observed percentage of successful removal is 60%	Updated to reflect realistic expectations of effectiveness in a real-world setting.
Section 11.2	Not included	New section on withdrawal for non- compliance (e.g. missed rebanding)	Ensures clear criteria for withdrawal tied to study adherence.

TABLE OF CONTENTS

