2.2. Purpose of Investigative Study

The aim of this study is to investigate the safety and effectiveness of a mechanical device to remove skin tags in adults. The device utilizes the ligation method by applying a silicone band around the base of a skin tag, therefore restricting the blood supply, which is vital to its growth and survival. Because this method does not include freezing or burning of tissue in or around the skin tag, it could be considered less invasive and less risky than other options.

A clinical validation study to demonstrate the safe and effective removal of skin tags will be completed under the direction of an investigator (dermatologist or other health care professional) led protocol. This study will assess the proportion of skin tags successfully removed within a 20-day period, and to evaluate associated safety outcomes. Adult (22 years and above) subjects fitting the inclusion/exclusion criteria will be recruited, given they have one or more skin tags consistent with device labeling. All subjects entering the clinical study will have the device applied by the healthcare professional and proceed through the study, recording their experience using an electronic clinical diary to collect data.

Since this device is to be sold over-the-counter, evaluation of the subject's self-selection and label comprehension abilities will be completed under a separate Human Factors and Usability study and is therefore not required in the scope of this clinical trial.

3

³ UC Davis Dermatology Online Journal

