3. STUDY DEVICE NAME AND DESCRIPTION

3.1. Study Device Name: Skin Tag Remover (STR)

For this Protocol, the study device will be referred to as "Skin Tag Removal" study device or "STR" study device. There are two versions of the STR study device, automatic and manual. Each version is also manufactured in two sizes which correspond to the size of the skin tag to be removed.

Under protocol version 1, t he smaller size (to be referred to as "micro" for the remainder of this document) is designed to be used with skin tags having a base measuring between 2–4mm. The larger size (to be referred to as "standard" for the remainder of the document) is to be used with tags having a base measuring between 4–6 mm.

Under protocol version 2, the micro size band will be used on all skin tags measuring between 4-6mm. The standard size will no longer be used and skin tags measuring between 2-4mm will not be enrolled.

Product labeling has a helpful guide for determining size of band to use. All four versions function in the same manner by placing a band at the base of the skin tag, therefore, this document will collectively refer to all four iterations of the study device as "STR."

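### Section 6.2.6.1 reports removal by micro versus standard without separating protocol version, so band size is confounded with follow-up, bandage, rebanding and tag size

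*Protocol*

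**What the plan says.** Section 6.2.6.1 lists the splits by which performance will be reported. One is "Band size (micro vs. standard". The efficacy row of the same section adds that in all cases "the removal rate will be categorized by skin tag size (micro or standard", together with body location and demographics. Protocol version is not among the splits. The section also states: "Data collected will be captured and archived using a per-protocol approach".

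The endpoint window is in Section 2.2: "This study will assess the proportion of skin tags successfully removed within a 20-day period".

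Section 3.1 says of Version 2: "The standard size will no longer be used and skin tags measuring between 2-4mm will not be enrolled". All standard-band tags are therefore Version 1 tags. The version table at the front of the protocol records how Version 1 tags were handled: "Daily eDiaries Day 1-10", "Virtual Visit 3 window Day 11-14", no bandage, and "Rebanding not permitted; participants were withdrawn if device detached prematurely". Under Version 2 the diaries run to Day 20, Visit 3 falls on Days 21-24, each tag is bandaged, and up to two rebandings per tag are allowed (Sections 6.2.1, 6.2.3 and 6.2.4).

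The current text keeps the Version 1 tags in the study. Section 6.1 describes about two thirds of subjects on micro bands, over a tag range of 2-6 mm that only both versions together cover, and one third on standard bands. Section 6.2.1 says Version 1 used the two sizes in roughly equal numbers.

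**The concern.** A split by band size is read as showing what the band does. Here the standard group sits wholly in one version and the micro group straddles two, and the versions differ in ways that bear on removal. The sponsor's own reasons for the changes say so: diaries were lengthened because tags may come off after Day 10, and bandages were added to keep bands in place. The 20-day endpoint was not followed in the daily diary for any standard-band tag.

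Tag size is a second confounder. In Version 1 the band followed the base width (micro 2-4 mm, standard 4-6 mm), so even a comparison within that version is of band plus tag size.

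The labels also collide. Section 6.2.1 calls a 4-6 mm tag standard by size, while Version 2 bands it with micro. The same Version 2 tag can thus be micro in one split of Section 6.2.6.1 and standard in the other. On either reading, one side of each split mixes versions and the other does not.

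At stake is how the result is read. The indication statement is to be settled after the study, and a difference produced by observation time and handling could be taken for a difference between bands.

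**Working it through.** The protocol gives no effect size, power or sample size for micro versus standard, so there is no stated figure to reproduce. The check asks what the band-size split would show if the two bands were identical.

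**Inputs from the protocol**
- 60% removed (Section 6.1), taken here as the Day 20 rate; 200 tags in total (Section 6.2.1).
- Version 1 about 1:1 micro to standard (Section 6.2.1).
- Overall micro to standard 3:1 (version table) or about 2:1 (Section 6.1). Both are used as a range.

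**Assumptions, not in the protocol**
- F10, the proportion off by Day 10. A constant daily hazard gives F10 = 1 − 0.4^(10/20) = 36.8%. The values 50% and 55% are also used.
- The 200 tags cover both versions.
- No effect of tag size or bandage.

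**Group sizes**
- 3:1: 50 standard, 50 Version 1 micro, 100 Version 2 micro. Version 2 is 2/3 of the micro group.
- 2:1: about 67 in each. Version 2 is 1/2 of the micro group.

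**Gap from diary follow-up alone**

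Standard rate = F10. Pooled micro rate = w × 60% + (1 − w) × F10, where w is the Version 2 share. Gap = w × (60% − F10).

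| F10 | 3:1 (w = 2/3) | 2:1 (w = 1/2) |
|---|---|---|
| 36.8% | 52.3% vs 36.8%: +15.5 points | 48.4% vs 36.8%: +11.6 points |
| 50% | +6.7 | +5.0 |
| 55% | +3.3 | +2.5 |

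**Adding band loss**

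Let d be the share of tags losing the band (10-30%) and r the removal rate after rebanding (30-60%), both assumed. F10 runs from 36.8% to 60%; at 60%, nothing comes off after Day 10.
- Version 2 rate = (1 − d) × 60% + d × r.
- Version 1 rate = (1 − d) × F10 if withdrawn tags count as failures, or F10 if they leave the denominator.

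Counted as failures, micro is ahead in every scenario run, by 1.5 to 22.8 points. Excluded, the range is −6.7 to +17.2 points.

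The lower end, at 3:1 with F10 = 60%, d = 30% and r = 30%:
- Version 2 = 0.7 × 60% + 0.3 × 30% = 51%.
- Pooled micro = (35 × 60% + 100 × 51%) / 135 = 53.3%.
- Standard = 60%, so the gap is −6.7 points.

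**Check of a common cut-off**

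Count removal by Day 10 on the first band, with every treated tag in the denominator. Both versions then give (1 − d) × F10. With d = 20% and F10 = 50%, that is 40% in each and the gap is zero, provided bandages do not change d.

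**The case against.** **The micro group is not only Version 2.** A reader might set the standard tags against Version 2 micro tags and quote 60% − 36.8% = 23.2 points. The protocol does not plan that comparison. Its micro group also holds Version 1 tags on 2-4 mm bases, with the same 10-day diary, no bandage and no rebanding. This stands, and it dilutes the constant-hazard gap to 11.6-15.5 points.

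**The direction is not fixed.** A reader might also infer that the split is bound to favour micro. The documents do not support that. They give no fall-off curve or detachment rate, and the per-protocol wording leaves open whether withdrawn Version 1 tags count. If they are dropped, the sign can reverse. Re-enrolment of Version 1 participants after device failure may also pull against micro. This stands too.

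**Ten days is not all the observation there was.** The version table lists no change to the Day 30 photo visit, so the 10 days describe diary tracking only. That is correct. But Section 6.2.6.1 draws efficacy from case report forms and diaries through Day 20. In the current text, a tag still present at Visit 3 may be excised or have its band taken off, so a later photo cannot reliably supply a 20-day device result.

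**This is a descriptive subgroup with no test or claim attached, and its details belong in the SAP.** No passage ties the indication to micro outperforming standard, and the study goal is 60% removal in each of the manual and automatic arms. This limits the seriousness. It does not remove the point, because the protocol itself fixes the two splits; an analysis that follows it as written produces the confounded figure.

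**Conclusion.** The point holds as one of confounding. Band size in Section 6.2.6.1 is entangled with protocol version and with tag size, so the pooled micro-versus-standard result cannot be read as a band effect.

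The likely direction favours micro. With identical bands and 60% removed by Day 20, the diary window alone gives about 12-16 points under a constant hazard, 5-7 if 50% are off by Day 10, and 2.5-3.3 if 55% are. These figures rest on an assumed fall-off curve and on the 3:1 or 2:1 shares. Once band loss is included, the size and even the sign depend on how withdrawn Version 1 tags are counted.

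Neither a certain advantage for micro nor a 23-point gap in the planned split is supported. The change is worth making because it uses data already collected, but no primary conclusion depends on it.

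**What to change.** In Section 6.2.6.1:

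1. Replace both pooled splits, by band size and by skin tag size, with results by protocol version. Give tag size in millimetres so that micro and standard refer to the band only.
2. Label the Version 1 micro-versus-standard contrast as band plus tag size.
3. State the 20-day removal rate for Version 2 tags only.
4. For any display across versions, use removal by Day 10 on the first band. Keep all treated tags in the denominator, and count tags that lost the band or were withdrawn as not removed. Add a note that bandage use still differs.

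The Version 2 daily eDiary already covers Day 10, so no new data are needed. The cost is revised wording and one extra table. The sponsor also gives up any micro-versus-standard conclusion across versions, which this design cannot provide.
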